### **10.3 Shipping Instructions**

All samples will be shipped in compliance with the International Air Transport Association Dangerous Goods Regulations. All shipments should be batch shipped once a week, Monday through Friday, after communication with the receiving site.

Whole blood and FFPE biopsy specimens (including archival biopsy samples) will be shipped at refrigerated temperature (4°C). All other specimens (the remaining two biopsy samples, Research

Plasma, Research Blood PKs, and Research Urine PKs) will be packed in sufficient dry ice to last during transport for 3 days, and shipped or transported from the study site to:

[name]  
[name]  
Georgetown University Medical Center  
[name]  
[name]  
[contact]  
[contact]  
Email: [contact]

#### **10.4 Tissue Banking**

The biopsy samples will be labeled appropriately with the study protocol number, subject number, the date of collection, study time point, and location of collection (GUH or UPR) and stored at [name] laboratory in a -80° Freezer. FFPE biopsy specimens will be stored at room temperature.

Biological specimens collected during the conduct of each clinical trial that are not used during the course of the study will be considered deliverables under the contract and thus the property of the NCI. At study completion, NCI reserves the option to either retain or relinquish ownership of the unused biologic specimens. If NCI retains ownership of specimens, the Contractor shall collect, verify and transfer the requested biologic specimens from the site to a NCI-specified repository or laboratory at NCI's expense.

### **11. REPORTING ADVERSE EVENTS**

**DEFINITION:** AE means any untoward medical occurrence associated with the use of a drug in humans, whether or not considered drug related. An AE can therefore be any unfavorable and unintended sign), symptom, or disease temporally associated with participation in a study, whether or not related to that participation. This includes all deaths that occur while a participant is on a study.

Please note that all abnormal clinical laboratory values that are determined to be of clinical significance based on a physician's assessment are to be reported as AEs. Those labs determined to be of no clinical significance or of unknown clinical significance (per the physician's assessment) should not be reported as AEs. Any lab value of unknown clinical significance should continue to be investigated/followed-up further for a final determination, if possible.

A list of AEs that have occurred or might occur can be found in §6.2 Reported Adverse Events and Potential Risks, as well as the Investigator Brochure or package insert.

#### **11.1 Adverse Events**

##### **11.1.1 Reportable AEs**

All AEs that occur after the informed consent is signed and baseline assessments are completed must be recorded on the AE CRF (paper and/or electronic) whether or not related to study agent.

#### 11.1.2 AE Data Elements:

The following data elements are required for AE reporting.

- AE verbatim term
- NCI Common Terminology Criteria for Adverse Events version 4.0 (CTCAE v4.0) AE term (MedDRA lowest level term)
- CTCAE (MedDRA) System Organ Class (SOC)
- Event onset date and event ended date
- Treatment assignment code (TAC) at time of AE onset
- Severity grade
- Attribution to study agent (relatedness)
- Whether or not the event was reported as a SAE
- Whether or not the subject dropped due to the event
- Outcome of the event

#### 11.1.3 Severity of AEs

11.1.3.1 Identify the AE using the CTCAE version 4.0. The CTCAE provides descriptive terminology (MedDRA lowest level term) and a grading scale for each AE listed. A copy of the CTCAE can be found at

[http://ctep.cancer.gov/protocolDevelopment/electronic\\_applications/ctc.htm](http://ctep.cancer.gov/protocolDevelopment/electronic_applications/ctc.htm)

AEs will be assessed according to the grade associated with the CTCAE term. AEs that do not have a corresponding CTCAE term will be assessed according to the general guidelines for grading used in the CTCAE v4.0 as stated below.

#### **CTCAE v4.0 general severity guidelines:**

| Grade | Severity  | Description   |
|--------------|------------------|--|
| 1            | Mild             | Mild; asymptomatic or mild symptoms; clinical or diagnostic observations only; intervention not indicated.   |
| 2            | Moderate         | Moderate; minimal, local or noninvasive intervention indicated; limiting age-appropriate instrumental activities of daily living (ADL)*.                                 |
| 3            | Severe           | Severe or medically significant but not immediately life-threatening; hospitalization or prolongation of hospitalization indicated; disabling; limiting self-care ADL**. |
| 4            | Life-threatening | Life-threatening consequences; urgent intervention indicated.  |
| 5            | Fatal            | Death related to AE.   |

#### **ADL**

\*Instrumental ADL refers to preparing meals, shopping for groceries or clothes, using the telephone, managing money, *etc.*

\*\*Self-care ADL refers to bathing, dressing and undressing, feeding self, using the toilet, taking medications, and not bedridden.

#### 11.1.4 Assessment of relationship of AE to treatment

The possibility that the AE is related to study agent will be classified as one of the following: not related, unlikely, possible, probable, definite.

#### 11.1.5 Follow-up of AEs

All AEs, including lab abnormalities that in the opinion of the investigator are clinically significant, will be followed according to good medical practices and documented as such.

### 11.2 Serious Adverse Events

11.2.1 DEFINITION: Regulations at 21 CFR §312.32 (revised April 1, 2014) defines an SAE as any untoward medical occurrence that at any dose has one or more of the following outcomes:

- Death
- A life-threatening AE
- Inpatient hospitalization or prolongation of existing hospitalization
- A persistent or significant incapacity or substantial disruption of the ability to perform normal life functions
- A congenital anomaly or birth defect
- Important medical events that may not be immediately life-threatening or result in death or hospitalization should also be considered serious when, based upon appropriate medical judgment, they may jeopardize the patient and may require intervention to prevent one of the other outcomes.

#### 11.2.2 Reporting SAEs to DCP

11.2.2.1 The Lead Organization and all Participating Organizations will report SAEs on the DCP SAE Report Form found at <http://prevention.cancer.gov/clinical-trials/clinical-trials-management/protocol-information-office/pio-instructions-and-tools/2012-consortia>.

11.2.2.2 Contact the DCP Medical Monitor by phone within 24 hours of knowledge of the event.

DCP Medical/Task Order Monitor  
[name] [name], FACS  
NCI/Division of Cancer Prevention  
[name]

[name]  
[name]  
[contact]  
[contact]  
Email: [[contact]](mailto:[contact])

Include the following information when calling the Medical Monitor:

- Date and time of the SAE
- Date and time of the SAE report
- Name of reporter
- Call back phone number
- Affiliation/Institution conducting the study
- DCP protocol number
- Title of protocol
- Description of the SAE, including attribution to drug

11.2.2.3 The Lead Organization and all Participating Organizations will email written SAE reports to the following within 48 hours of learning of the event, using the fillable PDF SAE Report Form.

- DCP's Regulatory Contractor CCS Associates, Inc. (CCSA; [contact]) at [[contact]](mailto:[contact])
- DCP Medical Monitor, [name] ([[contact]](mailto:[contact]))
- Northwestern Cancer Prevention Consortium ([[contact]](mailto:[contact]))
- The Protocol PI, [name] ([[contact]](mailto:[contact]))

11.2.2.4 The DCP Medical Monitor and CCSA regulatory and safety staff will determine which SAEs require FDA submission as IND safety reports.

11.2.2.5 The Lead Organization and all Participating Organizations will comply with applicable regulatory requirements related to reporting SAEs to the IRB/IEC.

### 11.2.3 Follow-up of SAE

Site staff should send follow-up reports as requested when additional information is available. Additional information should be entered on the DCP SAE Report Form in the appropriate format. Follow-up information should be sent to DCP as soon as available. The length of time for follow-up of an SAE is 6 months.

## 12. STUDY MONITORING

### 12.1 Data Management

Data will be managed by the study statistician, [name], according to standard operating procedures, which meet the guidelines of DCP Requirements for Data Management and which follow the Data Management Plan that Northwestern University has on file with the Division of Cancer Prevention, NCI. The Consortia 2012 Data Management Plan, submitted as part of a

contract agreement with the NCI (HHSN261201200035I), was approved.

## **12.2 Case Report Forms**

Participant data will be collected using protocol-specific case report forms (CRFs) developed from the standard set of DCP Chemoprevention CRF Templates and utilizing NCI-approved Common Data Elements (CDEs). The approved CRFs will be used by Northwestern University to create the electronic CRF (e-CRF) screens in the Robert H. Lurie Comprehensive Cancer Center of Northwestern University (Lurie Cancer Center) Clinical Trials Management System (CTMS). Accrual-site staff will enter data into the e-CRFs for transmission to DCP according to DCP standards and procedures.

## **12.3 Source Documents**

All source documents will be collected and stored in the Clinical Research Office of the site where the participant was accrued. Any data recorded directly on CRFs that constitute no prior written or electronic record of data, will be specifically identified as source data.

## **12.4 Data and Safety Monitoring Plan**

A comprehensive Data Safety and Monitoring Plan has been submitted by Northwestern University, approved by the DCP, and is on file there. This study will be subject to Northwestern Data Monitoring Committee review according to the Master DSMP. Any future changes will be forwarded for review.

As part of our Master DSMP, this study will be reviewed semi-annually by a Data Monitoring Committee. This semi-annual report includes a list of all reported adverse events, serious adverse events, dose limiting toxicities, and protocol deviations.

Adverse events are reviewed monthly by the NCI DCP medical monitor through the submission of the Minimum Data Set.

## **12.5 Sponsor or FDA Monitoring**

The NCI, DCP (or their designee), pharmaceutical collaborator (or their designee), or FDA may monitor/audit various aspects of the study. These monitors will be given access to facilities, databases, supplies and records to review and verify data pertinent to the study.

## **12.6 Record Retention**

Clinical records for all participants, including CRFs, all source documentation (containing evidence to study eligibility, history and physical findings, laboratory data, results of consultations, *etc.*), as well as IRB records and other regulatory documentation will be retained by the Investigator in a secure storage facility in compliance with Health Insurance Portability and Accountability Act (HIPAA), Office of Human Research Protections (OHRP), Food and Drug Administration (FDA) regulations and guidances, and NCI/DCP requirements, unless the standard

at the site is more stringent. The records for all studies performed under an IND will be maintained, at a minimum, for two years after the approval of a New Drug Application (NDA). For NCI/DCP, records will be retained for at least three years after the completion of the research. NCI will be notified prior to the planned destruction of any materials. The records should be accessible for inspection and copying by authorized persons of the Food and Drug Administration. If the study is done outside of the United States, applicable regulatory requirements for the specific country participating in the study also apply.

## **12.7 Cooperative Research and Development Agreement (CRADA)/Clinical Trials Agreement (CTA)**

N/A

## **13. STATISTICAL CONSIDERATIONS**

### **13.1 Study Design/Description**

We propose a single-arm, multicenter MTD seeking, escalation study. To meet our primary goal, 2-48 participants with cirrhotic livers expressing high levels (score 3 and above) of  $\gamma$ -OHPdG ( $\gamma$ -OHPdG-high) in their baseline biopsy are required for the Polyphenon E intervention portion of the study.

In our unpublished data, 68 participants with cirrhosis, 38% (90% confidence interval, range 0.28, 0.49) of cirrhotic liver biopsies demonstrated high  $\gamma$ -OHPdG levels (IHC score  $\geq 3$ ). Therefore, a minimum of 4 and maximum of 171 participants with liver cirrhosis will be screened in our current study. A minimum of 2 and a maximum of 48 participants whose cirrhotic liver biopsies show a  $\gamma$ -OHPdG score  $\geq 3$  will be registered for treatment. If a maximum tolerated dose is established, a total of 24 participants will receive the maximum tolerated dose. The maximum tolerated dose is defined as the highest dose where no more than 1 of 6 participants experience an event meeting the Discontinue Therapy Criteria (DTC) during the first four weeks of treatment and the next higher dose is such that 2 or more participants had experienced an event meeting the DTC during the first four weeks of treatment.

Trial enrollment was stopped early, with 13 patients enrolled in Cohorts 1- 4 during dose escalation, of whom 10 participants had both pre- and post-treatment biopsies for biomarker assessment (Table 6). No participants were enrolled in the dose expansion cohort.

**Table 6:** Trial Enrollment

| Cohort         | Started Trt | Pre & Post Bx | DTC |
|-----------------------|--------------------|--------------------------|------------|
| Cohort 1 (400mg QD)   | 3                  | 3                        | 0          |
| Cohort 2 (400 mg BID) | 3                  | 3                        | 0          |
| Cohort 3 (600 mg BID) | 3                  | 2                        | 0          |
| Cohort 4 (800 mg BID) | 4                  | 2                        | 1          |

### **13.2 Randomization/Stratification**

There is no randomization in this study.

### 13.3 Accrual and Feasibility

The following strategies will be applied to ensure complete enrollment within the first twelve months of study initiation:

MedStar Georgetown Transplant Institute is a network of multidisciplinary teams that provides medical care to participants with chronic liver disease. This network includes GUH, Washington Hospital Center (WHC), Franklin Square Medical Center, and MedStar Georgetown Transplant Institutes in Fairfax and Frederick. The network serves about 2,200 participants with chronic liver disease each year. Drs. [name], [name], and [name] have weekly clinics in MedStar GUH, WHC, and Georgetown Transplant Institute in Fairfax. When they identify potential candidates at any of the sites (pre-screen), these participants will be screened for the study at MedStar GUH (screen 1 and 2) and registered if indeed eligible. The distance between MedStar Georgetown Transplant Institute in Fairfax and MedStar GUH is 17 miles (a 25 minute drive by car), and the distance between MedStar WHC and GUH is 5 miles (a 15 minute drive by car); these distances allow participants relatively easy travel from MedStar Georgetown Transplant Institute in Fairfax or WHC to GUH for medical care.

Potential candidates from Franklin Square Medical Center and transplant clinic at Frederick will also be referred to GUH for this study. Among the 2,200 hepatology participants seen under the MedStar Network within one year, approximately 20% have compensated cirrhosis without liver cancer. Therefore we have a pool of 440 participants that meet the eligibility criteria for this study. Based on our small 50-patient survey, 90% of participants should be interested in participating in the study, despite having to undergo liver biopsy. Thus we have a pool of 400 participants per year from which to draw potential study candidates.

At UPR, over 1000 participants are seen annually over the hepatology clinical enterprise. It is estimated that approximately 50% of these participants have underlying cirrhosis at different stages, including pre-transplant participants. [name] estimates that 10% of cirrhotic individuals may be eligible for the study translating to approximately 50-100 participants providing adequate numbers for screening into the study.

One study coordinator will be shared by Drs. [name] and the investigator's at Georgetown for participant enrollment and follow-up in Washington DC. One or two specific days of the week can be assigned to each physician for seeing participants enrolled onto this study, so the study coordinator will be able to follow all participants enrolled in Washington DC. Monthly teleconferences will be arranged for Drs. [name], [name], and the study coordinators to discuss enrollment and study related issues.

With these prescreening and rolling enrollment strategies, we believe that we will be able to screen 171 participants with liver cirrhosis in order to be able to find 48 participants whose cirrhotic liver biopsies show a  $\gamma$ -OHPdG score  $\geq 3$  by IHC ( $\gamma$ -OHPdG-high) to be enrolled into the pilot study within the first year.

Our strategies are to prescreen most participants by medical record review after the protocol is approved, obtain consent, and, if needed, obtain a baseline biopsy from most participants within the first few months of study initiation so that candidates for intervention enrollment are identified quickly. From the pool of study candidates, we plan to enroll 6 participants per month if. With this plan, even if there are delays for any reason, we will be able to complete the study within two years.

We plan to allow up to three weeks from the day of biopsy to obtain the liver  $\gamma$ -OHPdG score. The liver samples will be batched and tested twice per month. If the rate of cirrhotic liver biopsies with a  $\gamma$ -OHPdG score  $\geq 3$  is lower than expected, we will increase the number of subjects that are pre-screened per month.

### **13.4 Primary Objective, Endpoint(s), Analysis Plan**

The primary objectives are to establish MTD, collect safety data of Polyphenon E/EGCG at MTD treatment in participants with cirrhosis and to determine the suppressing effects of /Polyphenon E/EGCG treatment on  $\gamma$ -hydroxy-1,N(2)-propanodeoxyguanosine ( $\gamma$ -OHPdG)levels in cirrhotic liver.

To assess the safety of Polyphenon E treatment in participants with cirrhosis, we will list all the adverse events and provide summary statistics.

To explore possible effects of Polyphenon E treatment on  $\gamma$ -OHPdG levels in cirrhotic liver samples of participants known to have high levels in liver biopsy samples.

The primary study objective is to assess the effect of Polyphenon E treatment on  $\gamma$ -OHPdG expression. Based on our preliminary data, we expect a 30-40% decrease in  $\gamma$ -OHPdG expression in cirrhotic liver after six months of Polyphenon E treatment. Twenty-four subjects with high  $\gamma$ -OHPdG levels in their liver biopsies will receive Polyphenon E. This provides 80% or greater statistical power to confirm a 30% or bigger decrease in  $\gamma$ -OHPdG levels at a 0.05 alpha level with a two sided test, and coefficient of variation = 50%-100%. We will use a nonparametric Wilcoxon test to compare the post-pre differences to zero. We anticipate that high pre-therapy IHC scores = 3, 4 and 5 vs. post-therapy scores mean = 2, —using a pre-therapy average of 4 to be conservative. Thus we will have two scores per person. The difference between Before and After = Before - After = B-A should be on average = 0 if treatment has no effect and on average about 1.33 and 1.60 after treatment = reduction of 33% and 40% respectively, down from 4.

Under usual assumptions of  $\text{corr}(B,A) = 0.5$  and  $SD(B) = SD(A)$  we get mathematically  $SD(B-A) = SD(B) = SD(A) = 2$ .  $SD=2$  was selected so as to give  $CV=100\%$  when  $mean = 2$  and  $CV=50\%$  when  $mean = 4$ .

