### **Numeric Results for Wilcoxon Test (Normal Distribution)**

Null Hypothesis:  $\text{Mean0}=\text{Mean1}$     Alternative Hypothesis:  $\text{Mean0}\neq\text{Mean1}$

Unknown standard deviation.

| Power   | N  | Alpha | Beta    | Mean0 | Mean1 | SD | Effect Size |
|---------|----|-------|---------|-------|-------|----|-------------|
| 0.84466 | 24 | 0.05  | 0.15534 | 0     | 1.33  | 2  | 0.665       |
| 0.94694 | 24 | 0.05  | 0.05306 | 0     | 1.6   | 2  | 0.8         |

Safety and adverse event data will be summarized using descriptive (frequency, %) statistics by dose cohort. The primary endpoint of MTD cannot be established because the study was closed early, and, based on the observed safety profile with a single DTC occurring in dose cohort 4 (1/4 patients), future studies can consider dose level 3 as the starting dose.

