fraction of participants with liver cirrhosis that have high levels of  $\gamma$ -OHPdG is calculated based on the number of subjects enrolled over the number of subjects screened based on the levels of  $\gamma$ -OHPdG in their first liver biopsy. This important information may help to estimate the portion of cirrhotic participants with high risk for HCC development, and can be used to design a future large chemoprevention study using Polyphenon E or other green tea extract in HCC prevention.

Due to the early stopping, secondary and exploratory endpoints will be summarized using descriptive statistics across dose cohorts. Changes in biomarkers across dose levels will be analyzed using a nonparametric trend test.

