### **13.6 Reporting and Exclusions**

We expect that we will identify an MTD from the 3+3 dose escalation cohort, then move to dose expansion cohort.

We expect that 2 to 48 subjects will have complete data on the primary endpoint. Main analysis will be based on the complete data. Additional descriptive analysis may be performed to see if dropouts show a systematic property. Thus, we expect the 15% of data missing values will be studied to determine possible patterns and dependence with other relevant variables.

We will report the reasons for any missing outcomes to determine if they may be related to the unobserved outcome. We will write a cautionary note that results could be biased if there is a background change in  $\gamma$ -OHPdG over time that is unrelated to Polyphenon E treatment.

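### Section 13.4 still claims 80% or greater power from 24 subjects for the primary IHC comparison, although 10 pre/post pairs were obtained and the early-closure text leaves this claim unqualified

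*Combined protocol and SAP*

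**What the plan says.** Section 13.4 names the effect on liver γ-OHPdG as the primary study objective. It expects a fall of 30-40% and plans for 24 subjects, and then states "This provides 80% or greater statistical power to confirm a 30% or bigger decrease", two-sided at 0.05. The test is given as "We will use a nonparametric Wilcoxon test to compare the post-pre differences to zero". The inputs are a pre-therapy mean of 4, mean falls of 1.33 and 1.60 points, equal before and after SDs of 2, and a correlation of 0.5, so the SD of the difference is also 2. The first row of the power table reads "0.84466 | 24 | 0.05" (power, N, alpha) for a difference of 1.33; the second gives 0.94694 for 1.60.

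Directly below that table the current text adds "The primary endpoint of MTD cannot be established because the study was closed early". Section 13.1 reports 13 patients enrolled in Cohorts 1-4, "of whom 10 participants had both pre- and post-treatment biopsies for biomarker assessment". Its Table 6 splits the pairs 3, 3, 2 and 2 by dose cohort, and the section adds "No participants were enrolled in the dose expansion cohort". Section 13.5 says "Due to the early stopping, secondary and exploratory endpoints will be summarized using descriptive statistics across dose cohorts" and then specifies a nonparametric trend test for biomarker changes across dose levels.

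On the analysis set, section 13.6 says "Main analysis will be based on the complete data", while section 13.8 places every sample from every treated subject in the primary analysis.

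**The concern.** The power claim rests on 24 subjects who, by section 13.1, were to receive the MTD. No MTD was established and nobody entered the expansion cohort. The early-closure text was added in three places: section 8.1, section 13.4 directly below the power table, and section 13.5. None of the three says what becomes of the primary IHC comparison or of its stated power.

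What is at stake is how a null result is read. A non-significant Wilcoxon result from 10 pairs could be set against a power of 80% or more that belongs to 24 subjects at one dose. The 10 pairs also pool four doses, with two or three pairs at each, so the pooled test asks a different question from the one that was powered.

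A smaller point concerns the claim itself. The text says 30%, but the smallest fall in the table is 1.33/4 = 33%.

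**Working it through.** **Inputs.** From section 13.4: N = 24, two-sided alpha 0.05, baseline mean 4, SD of the difference 2, mean differences 1.33 and 1.60. From section 13.1: 3 + 3 + 2 + 2 = 10 pairs. From sections 4.1.7 and 13.5: treated participants have a baseline score of 3 or more on a 0-6 scale.

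**1. Reproduce the table.** The one-sample noncentral-t power, with N reduced by the Wilcoxon efficiency for normal data, uses n' = floor(3N/π), df = n' − 1 and noncentrality = (difference/SD) × √n'. For N = 24, 3 × 24/π = 22.9, so n' = 22.
- Difference 1.33: 0.665 × √22 = 3.119, power 0.8447 (table 0.84466).
- Difference 1.60: 0.80 × √22 = 3.752, power 0.9469 (table 0.94694).

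Both rows match, so the plan's method is identified and its table is right.

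**2. The claimed 30% fall at N = 24.** 30% of 4 is 1.20, an effect size of 0.60. Noncentrality is 0.60 × √22 = 2.814 and power is **0.765**. The exact signed-rank test, simulated with normal differences, gives about 0.79, and an unadjusted paired t-test gives 0.804. By the plan's method 25 subjects give 0.785 and 26 give 0.804.

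**3. Ten pairs, plan's SD of 2.** 3 × 10/π = 9.55, so n' = 9.

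| Fall from 4 | Difference | Noncentrality | Power, 10 pairs | Power, N = 24 |
|---|---|---|---|---|
| 30% | 1.20 | 1.800 | 0.354 | 0.765 |
| 33% | 1.33 | 1.995 | 0.419 | 0.845 |
| 40% | 1.60 | 2.400 | 0.559 | 0.947 |
| 50% | 2.00 | 3.000 | 0.748 | 0.994 |

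The 50% row is included because section 13.4 also anticipates a post-therapy mean of 2, down from 4. Exact signed-rank simulation at 10 pairs gives 0.38, 0.45 and 0.60 for the first three rows. With SD 2, power of 0.80 at 10 pairs needs a difference of about 2.13, which is 53% of 4.

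**4. How far this depends on the SD.** For scores between 3 and 6 with mean 4, the variance is at most (4 − 3) × (6 − 4) = 2, so the baseline SD is at most √2 = 1.41. Under the plan's assumptions of equal SDs and correlation 0.5, the SD of the difference equals the baseline SD. With 1.41 for the difference, 10 pairs give:
- 30%: noncentrality 2.546, power 0.608
- 33%: noncentrality 2.821, power 0.696
- 40%: noncentrality 3.394, power 0.843

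The SD of the difference at which 10 pairs just reach 0.80 is about 1.12, 1.25 and 1.50 for falls of 30%, 33% and 40%. The last of these lies above 1.41.

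**The case against.** The strongest objection is to the size. The SD of 2 sits badly with the plan's own eligibility rule. If the baseline SD cannot exceed 1.41 and the plan's other assumptions hold, 10 pairs exceed 80% power for a 40% fall. If baseline scores are only 3, 4 or 5 with mean 4, the SD is at most 1.0 and the three powers rise to 0.88, 0.94 and 0.99. This stands as a limit on what can be said. A reader might infer that 10 pairs flatly lack 80% power, and the documents do not establish that. Nor do they establish the opposite: post-therapy scores are not confined to 3-6, so their SD may exceed the baseline SD, and normal theory is approximate for a bounded score.

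A second objection is that the shortfall is disclosed and the power paragraph is only a design record. Section 13.1 does disclose the 10 pairs, so nothing is concealed. But section 13.4 does not mark its calculation as superseded, even though closure text was added directly beneath it.

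A third is that section 13.5 covers biomarkers in its trend test. That sentence follows one limited to secondary and exploratory endpoints, and it tests dose trend, not change from zero. A reader might also infer that the primary IHC change now has no defined analysis. That goes too far, since the Wilcoxon test can be run unchanged on 10 pairs.

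Finally, the shortfall at 30% is small and depends on the method. This is conceded.

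**Conclusion.** The point holds as a stale power statement. Section 13.4 attaches 80% or greater power to a sample that was not obtained, and no early-closure text corrects it. A reader might take this as an error in the power table. It is not, because both rows reproduce.

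In size, 10 pairs replace 24 subjects. Under the plan's stated SD of 2, power for the expected 30-40% fall is about 0.35 to 0.56, and about 0.75 if the mean falls to 2. If the SD of the difference is 1.41, the range for 30-40% is about 0.61 to 0.84. All of these figures assume normal differences and a baseline mean of 4. The wording about a 30% fall is slightly generous even for 24 subjects (0.765 by the plan's method).

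The conflict between sections 13.6 and 13.8 is a minor matter of wording. A paired test can use only the 10 participants with both biopsies.

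**What to change.** In section 13.4:
- Label the N=24 paragraph and table as the original design, not achieved.
- Limit the power claim to the 33% and 40% falls in the table, or restate the 30% figure as about 77%.
- State that the Wilcoxon test uses the 10 pairs pooled over four dose levels, that the 80% figure does not carry over to it under the plan's SD of 2, and that a non-significant result is not to be read against that figure.
- Report the paired change with a 95% CI beside the test, and list individual changes by dose. Section 13.5 already promises 95% intervals for estimates.

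In section 13.8, add that the paired analysis uses participants with both biopsies, in line with section 13.6. The reasons for the three missing pairs (13 − 10) are already due under section 13.6.

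The cost is a few sentences in 13.4 and one clause in 13.8, with no new participants, samples or procedures.
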